4.6.7. Prior and Concomitant Medications

Prior and concomitant medications will be coded using the WHO Drug Dictionary (March 2015 or later). Results will be tabulated by ATC and preferred term.

When there are partial or missing dates, imputed dates will be used to determine 1) if a medication is prior or concomitant, and 2) duration of exposure of alternative FAP treatment (tafamidis/diflunisal). Imputed dates will not be presented in the listings.

For medications with partial start or stop dates: the first day/month will be imputed for start date, and the last day/month will be imputed for stop date. For medications with a completely missing start date, the medications will be considered as started prior to the first dose of study drug; medications will be classified as prior, concomitant or both depending on the medication stop dates. For medications with a completely missing stop date, the end of study date will be imputed.

Prior and concomitant medications will be presented in data listings.

4.6.8. Ophthalmology Examinations

Ophthalmology examinations include Visual Acuity, Visual Field, Slit Lamp Biomicroscopy, Intraocular Pressure, Dilated Indirect Ophthalmoscopy, and Fundus Photography.

Visual Acuity, Visual Field, and Intraocular Pressure Results: The actual value and change from baseline results will be summarized.

Biomicroscopy (Slit Lamp) and Dilated Indirect Ophthalmoscopy Exam Results: For the baseline results, the number and percentage of patients falling into each category of the examination status (normal, abnormal/not clinically significant, abnormal/clinically significant) will be summarized for each eye structure. For post-baseline results, the number and percentage of patients falling into each category of the examination status (new findings/worsening of finding, no change, improvement of finding, etc.) will be summarized for each eye structure.

Abnormal fundus findings at baseline will be recorded in the medical history log. Treatment-emergent abnormal fundus findings that are considered clinically significant will be recorded in the AE log.

Data for each of these assessments will be provided in a data listing.

4.6.9. Suicidality Questionnaire

The number and percentage of patients experiencing the suicidal ideation, suicidal behavior, or self-injurious behavior composite outcomes (and individual components) will be summarized by visit. A shift table will be employed to summarize the baseline C-SSRS category versus the worst post-baseline C-SSRS category; the categories are defined as 1) no suicidal ideation or behavior, 2) suicidal ideation, and 3) suicidal behavior. Patients experiencing both suicidal ideation and suicidal behavior are included in the suicidal behavior category.

Data from the C-SSRS questionnaire will be provided in a data listing.

4.7. Anti-Drug Antibody

The number and percentage of patients with confirmed positive ADA assay results at any time point during study as well as at each scheduled visit will be summarized. The titer results for patients with confirmed positive ADA results will also be summarized using descriptive statistics.

For patients with confirmed positive ADA results, spaghetti plots for the serum TTR (ELISA) over time and the plasma concentration of ALN-18328, DLin-MC3-DMA and PEG2000-C-DMG over time will be presented. Effect of positive ADAs on efficacy and safety (e.g., IRRs) may also be explored.

Anti-drug antibody (ADA) data and patients with confirmed positive ADA results will be presented in data listings.

5. CHANGES TO PLANNED ANALYSES

The SAP version 2.0 includes more details previously not discussed in the original SAP version 1.0. The following major changes will be implemented in the SAP version 2.0 that are different from the planned analysis specified in the SAP version 1.0 and/or the protocol version 6.0.

This SAP Version 2.1 incorporates an additional change to censor data post alternative treatment for the analysis of NIS-W, which is documented in [Section 5.6](#).

5.1. Primary Analysis Method for Efficacy Endpoints

In the study protocol and the original SAP V1.0, the primary analysis method specified for the primary and secondary efficacy endpoints was the MI/ANCOVA. The original SAP V1.0 was submitted for FDA review (IND Serial # 0019). Following FDA's comment received on 02July2015 and the sponsor's responses on 31August2015, the primary analysis method for all efficacy endpoints will be changed to MMRM method. The history and rationales for the change of primary analysis method are described below. The change is aligned with the CHMP guideline on missing data in confirmatory clinical trials (EMA/CPMP/EWP/1776/99 Rev.1).

Mixed-effects model repeated measures and MI are 2 common methods for handling missing data in analysis of continuous, longitudinal endpoints. For this study, ANCOVA/MI was originally selected as the primary analysis, with MMRM as a key sensitivity analysis.

In the literature, MMRM and MI have been compared in several simulation studies. [Collins et al. \(2001\)](#) noted that the 2 methods yielded similar inference. However, [Barnes et al. \(2008\)](#) found a larger average standard error for MI relative to MMRM, suggesting that MI controls type I error conservatively and loses power to detect true treatment differences. [Siddiqui \(2011\)](#) compared MI/ ANCOVA and MMRM approaches using both simulated datasets and 25 New Drug Application (NDA) datasets of neuropsychiatric drug products, and concluded that MMRM appears to be a better choice in maintaining statistical properties relative to the MI approach when dealing with ignorable missing data.

For the ALN-TTR02-004 trial setting, we compared the properties of these 2 methods via simulation. Our results demonstrated that, while both methods control type I error, MMRM appears to be more powerful in detecting true treatment effect compared with ANCOVA/MI.

Moreover, [White et al. \(2012\)](#) argued that excessive focus on including all randomized patients with missing outcomes can lead to a choice of analysis that rests on implausible or unnecessarily complex imputation. The authors proposed that the main focus in choosing the primary analysis should be the plausibility of its assumptions, while inclusion of all randomized individuals is a requirement only for sensitivity analyses. The MI approach, which includes all randomized patients, is often designated as a sensitivity analysis.

Given these findings – and consideration of the complexity inherent when using the multistep MI approach, the primary analysis method will be changed to MMRM for the primary and secondary efficacy endpoints. MI/ANCOVA will be performed as the key sensitivity analysis for the primary endpoint and for the first secondary endpoint (Norfolk QOL).

5.2. Multiple Imputation/ANCOVA Method

The MI/ANCOVA method, as described in this document and in SAP V1.0, differs from that described in the current clinical protocol (Version 6: September 2015) in the MI method and in the explanatory covariates included in the (complete data) ANCOVA (discussed in [Section 5.4](#)).

The MI (for completely missing mNIS+7 assessments) described in the SAP differs from that in the clinical protocol in that 1) stepwise variable selection has been replaced with a pre-specified set of covariates to be included; 2) imputation is done separately by treatment arm. The rationale for these changes is outlined below.

- Stepwise variable selection was removed in order to simplify the analysis.
- The SAP specifies that imputation is done separately by study arm; the current protocol specifies that treatment assignment will not be included in the imputation. This change is motivated by simulations demonstrating a non-negligible loss in power when a single imputation model is employed and treatment is not included in the model; this loss in power is due to “cross-contamination” of imputation models between randomized arms [9].

In the protocol, the number of imputed datasets was specified as 100. In SAP V1.0, the number of imputed datasets was reduced to 10 following the conclusion that 3-5 imputations are often sufficient [10], however, in this SAP V2.0, the number of imputed datasets is increased to 100 to have more precise estimates.

5.3. Hierarchical Testing Order of Secondary Endpoints

In the protocol and SAP version 1.0, it was specified that secondary endpoints would be tested in the following order for the control of overall type I error: Norfolk QOL, NIS-W score, mBMI, 10-meter walk test, and COMPASS-31.

In this SAP amendment, R-ODS has been added as a secondary endpoint for controlled hypothesis testing, and 10-meter walk test has been moved up in the hierarchy. The revised list and order of secondary endpoints is the following: Norfolk QOL, NIS-W, R-ODS, 10-meter walk test, mBMI and COMPASS-31.

These changes were based on the Sponsor’s re-assessment of the clinical importance of these endpoints in hATTR amyloidosis patients.

5.4. Adjustment for Covariates in Statistical Models

The table below summarizes the history of changes in baseline covariates used in the statistical models.

Baseline Covariates	Protocol	SAP V1.0	SAP V2.0
	ANCOVA	ANCOVA	MMRM/ANCOVA
Baseline mNIS+7	X	X	X
Genotype (V30M vs. Non-V30M)	X		X
Genotype class (early onset V30M vs. Other)		X	
Age at hATTR symptom onset (< 50 vs. ≥ 50)			X
Previous tetramer stabilizer use (Yes vs. No)	X	X	X
Region (Western EU, North America, Rest of World)			X
Age at study entry as continuous variable	X		

Genotype class (early onset V30M vs. other) is one of the stratification factors at randomization. The early onset V30M subgroup includes patients who have the V30M genotype and were younger than 50 years old at hATTR amyloidosis symptom onset. At the time of this SAP amendment, the enrollment was complete and there were only 23 early onset V30M patients. Given the small sample size, the composite covariate “genotype class” is decomposed into 2 separate covariates “genotype” and “age at hATTR amyloidosis symptom onset.”

Region is added as a covariate because different rates of attrition and disease worsening were observed for different regions during blinded data monitoring. In addition, adding region may potentially address the influence of different non-V30M types observed across regions.

5.5. Binary Analysis of mNIS+7

In SAP V1.0, binary analysis of mNIS+7 included an analysis of patients with < 2-point increase in mNIS+7 change from baseline at Month 18. The 2-point threshold was originally used in the tafamidis Phase 3 trial in hATTR amyloidosis patients with polyneuropathy to define responders for the NIS-LL co-primary endpoint. That trial enrolled patients with very early stage neuropathy and mean baseline NIS-LL of approximately 8-11 points, in whom a 2-point worsening of NIS-LL was considered to be clinically meaningful. However, the patients enrolled onto this study have more advanced disease, with a mean baseline NIS of approximately 60 points, and the mNIS+7 primary endpoint is very different from NIS-LL, with a maximum score of 304 points compared to 88 points for NIS-LL. Therefore, a 2-point threshold was not deemed relevant for mNIS+7 change in this patient population.

In this SAP V2.0, 2 thresholds, < 10-point increase and any decrease (< 0-point change from baseline) will be employed to conduct the binary analysis of mNIS+7. These thresholds of < 10-point and < 0-point were chosen based on the 18-month estimated mNIS+7 progression rate observed in a natural history study of hATTR amyloidosis patients and the observed effect of patisiran on mNIS+7 at 18 months in the Phase 2 OLE study, respectively.

5.6. Censoring Data Post Alternative FAP Treatment

In this SAP V2.0, for the primary analysis of mNIS+7 and Norfolk QoL, the data post alternative FAP treatment will be censored. This censoring rule was not previously specified in the protocol or SAP V1.0. The rationale of adding this censoring rule is to eliminate the potential confounding effect caused by alternative FAP treatment. Sensitivity analyses for mNIS+7 and Norfolk QoL will be conducted including data post alternative FAP treatment.

In SAP V2.1, an update was made to apply the censoring rule to NIS-W as well so that the results will be consistent with the component analysis of mNIS+7.

For all other efficacy endpoints, the data will not be censored since no sensitivity analyses are planned.

5.7. Other Changes

Additional changes are listed in the table below.

Change from Protocol and/or SAP V1.0	Detailed Description/Rationale
In the protocol and original SAP V1.0, the first day of drug administration was designated as Day 0. In this SAP amendment and the TLF outputs, the first dose day will be defined as Day 1.	The change is made to follow CDISC convention. Each calculated study day after dosing is 1 day plus the reported study day following the protocol defined Schedule of Assessments.
In the protocol and original SAP V1.0, it was intended that an interim analysis for sample size re-estimation would be conducted; however, no interim analysis was conducted during the study.	In 2013, Berk et al. published results of a randomized placebo-controlled trial of diflunisal in FAP. This trial demonstrated that efficacy using a composite neurologic impairment score primary endpoint (NIS+7) could be established in a similar population with a similar study design and smaller study size (N=130). The sponsor believed that an interim analysis for sample size reassessment was therefore no longer necessary.
In SAP V2.0, dermal amyloid content is added as an exploratory endpoint.	In addition to IENFD and SGNFD, skin punch biopsies will also be assessed for dermal amyloid content, which has been added as an efficacy parameter in this SAP V2.0.
In SAP V2.0, the walk speed for patients unable to perform the walk will be imputed as 0.	The imputation algorithm is added to address the informative missing data for patients unable to perform the walk due to worsening of disease.
Renal clearance for siRNA and 4-dimethylaminobutyric acid (DMBA) will not be analyzed.	As per protocol, renal clearance for siRNA and 4-dimethylaminobutyric acid (DMBA) were to be determined whenever possible. Only sparse pre-dose urine collections (and volumes) were obtained in patients enrolled in this study on select days that patients returned to the clinic for dosing (Days 0, 21, 126, 252, 399, 546 and at time of early withdrawal). In order to estimate renal clearance, detailed serial urine and corresponding plasma collections that describe a time course of exposures in both matrices over a dosing interval within individual subjects are required. As it is not possible to reliably estimate the renal clearance for either siRNA or DMBA in individual patients using standard pharmacokinetic methods based on the limited urine and plasma sampling implemented in this outpatient study, renal clearance estimation for either analyte were not performed and cannot be reported for this study.

Change from Protocol and/or SAP V1.0	Detailed Description/Rationale
In SAP V2.0, the definition for cardiac subpopulation was added. This subpopulation was not previously defined in the protocol or in SAP V1.0.	In SAP V2.0, the cardiac subpopulation was defined in Section 4.2 as the following: the cardiac subpopulation will be comprised of patients with pre-existing cardiac amyloid involvement, defined as patients with baseline left ventricular (LV) wall thickness ≥ 1.3 cm and no aortic valve disease or hypertension in medical history.

7. APPENDICES

7.1. Detailed Statistical Methodology for Pattern Mixture Model

In the PMM analysis, similar to the primary analysis, mNIS+7 assessments performed after the initiation of alternative treatment for FAP will be treated as missing. For non-monotone missing data, the 9-month assessment will be imputed as the treatment group mean. The non-monotone missing data is expected to be rare.

As an initial step, an intermediate mNIS+7 dataset for all mITT patients will be prepared which will include the key variables listed in the table below.

Key Variables	Description
Patient number	Unique subject ID for each patient in mITT population
Treatment arm	Placebo or patisiran
Baseline variables	Including gender, genotype, age at ATTR onset, previous tetramer stabilizer use, region, KPS, FAP stage (I vs. II/III), and cardiac subpopulation.
Baseline mNIS+7 score	
mNIS+7 total score change from baseline at Month 9	Set as missing if a patient does not have 9-month data; If a patient has 18-month mNIS+7 but is missing 9-month (non-monotone missingness), the 9-month value will imputed as the treatment group mean.
On-treatment flag for Month 9	If 9-month assessment is non-missing: If assessment date – last dose date \leq 60 days, then flag = “yes” otherwise flag = “no” If 9-month assessment is missing: If Day 254 (scheduled 9-month visit) – last dose date \leq 60, then flag = “yes” otherwise flag = “no”
mNIS+7 total score change from baseline at Month 18	Set as missing if a patient does not have 18-month data
On-treatment flag for Month 18	If 18-month assessment is non-missing: If assessment date – last dose date \leq 60 days, then flag = “yes” otherwise flag = “no” If 18-month assessment is missing: If Day 554 (scheduled 18-month visit) – last dose date \leq 60, then flag = “yes” otherwise flag = “no”
Death flag	Flag = “yes” if a patient has missing 18-month mNIS+7 and death day \leq 561; otherwise flag = “no”

Step 1: For patients who have missing data and are alive before Month 18: imputation of missing data for the placebo arm and for the patisiran arm during the on-treatment period.

In the first step, missing data for the placebo arm and missing data for the patisiran arm during the on-treatment period will be imputed under the MAR assumption. Multiple imputation will be conducted among patisiran and placebo patients separately using a regression procedure, including the following covariates: baseline mNIS+7 score, genotype, age at ATTR onset, prior tetramer stabilizer use, region, KPS, FAP stage (I vs. II/III), cardiac subpopulation and gender.

The input dataset DATAIN will include a subset of the above dataset with Death Flag = “no.” For patisiran patients, the mNIS+7 data collected after treatment discontinuation will be excluded (set as missing). If Treatment Arm = “patisiran”:

- i) If On-Treatment Flag for Month 9 = “no” then mNIS+7 change at Month 9 will be set as missing.
- ii) If On-Treatment Flag for Month 18 = “no” then mNIS+7 change at Month 18 will be set as missing.

Below is a sample SAS code:

```
proc mi data=DATAIN out=DATA_STEP1 seed=234 nimpute=100;
  by treatment;
  monotone method=reg;
  var baseline_variables mNIS_BASE mNIS_chg_m9 mNIS_chg_m18;
run;
```

For patisiran arm, the imputed scores during the on-treatment period will be kept while the imputed scores after treatment discontinuation will be discarded and replaced by either observed non-missing values or imputed values described in the next step. In the output dataset DATA_STEP1, if Treatment Arm = “patisiran”:

- i) If On-Treatment Flag for Month 9 = “no” then mNIS+7 change at Month 9 will be replaced by the value in DATAIN.
- ii) If On-Treatment Flag for Month 18 = “no” then mNIS+7 change at Month 18 will be replaced by the value in DATAIN.

Denote this updated dataset as DATA_STEP1_2.

Step 2: For patients who have missing data and are alive before Month 18: imputation of missing data for the patisiran arm after treatment discontinuation.

In the second step, missing data for the patisiran arm after treatment discontinuation will be imputed using the PMM approach by creating control-based pattern imputation.

Below is a sample SAS code:

```
proc mi data=DATA_STEP1_2 out=DATA_STEP2 nimpute=1 seed=xxx;
  by _imputation_;
  class treatment;
  monotone method=reg;
  mnar model (mNIS_chg_m9 mNIS_chg_m18/modelobs=(treatment='placebo'));
  var baseline_variables mNIS_BASE mNIS_chg_m9 mNIS_chg_m18;
run;
```

Step 3: Imputation of missing data for patients who died before Month 18, regardless of treatment arm.

For patients with Death Flag = “yes,” missing 18-month mNIS+7 change from baseline scores will be imputed 100 times, using a random draw from the worst 10% 18-month mNIS+7 change scores among all non-missing values in the dataset DATAIN. Concatenate these records with DATA_STEP2, and sort by dataset number and patient number.

After step 3, each of the complete dataset will be analyzed by an ANCOVA model. The resulting estimates (LS means and standard errors) will be combined using SAS PROC MIANALYZE.

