3.8. Missing Data with Efficacy Endpoints

All efficacy data collected during study, regardless of whether before or after treatment discontinuation, will be included for analyses, with the exception of mNIS+7, Norfolk QOL, and NIS-W assessments collected post alternative FAP treatment (discussed in Section 3.7).

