- c. Patisiran patients who have missing data (either Month 9 or 18) after stopping their study treatment: Patients will no longer benefit from treatment in the future and will have trajectory similar to placebo patients. Therefore, missing data after treatment discontinuation (more than 60 days after last dose of study drug) will be imputed using the data from placebo patients.
2. Patients who die before Month 18 and have missing data: Assuming that deaths observed in the study will likely be related to worsening of disease, the missing data at Month 18 will be imputed by taking random samples from the worst 10% mNIS+7 change scores in the entire population. The imputation will be done for patients from both patisiran and placebo arms.

Missing values will be imputed 100 times to generate 100 complete datasets using procedures as described above. An ANCOVA model will be fit to each “complete” dataset for the change from baseline in mNIS+7 at Month 18. The ANCOVA model will include baseline mNIS+7 as a continuous covariate and treatment arm (patisiran vs. placebo), genotype (V30M vs. non-V30M), age at ATTR onset (Before age 50 vs. After age 50), previous tetramer stabilizer use (Yes vs. No), and region (Western Europe, North America, and Rest of World) as factors. The resulting estimates from the 100 analyses will be combined using Rubin’s formulae, and the 95% confidence interval will be constructed, similar to the procedure described in the MI/ANCOVA section.

More details on the implementation of PMM are discussed in Appendix 7.1.

Including Data Post Alternative Treatment for FAP

The primary analysis will not include mNIS+7 assessments performed after the initiation of alternative treatment for FAP (Section 3.7). Sensitivity analysis including data post alternative treatment for FAP will be conducted using the MMRM model. In this sensitivity analysis, all assessments will be used in the analysis regardless of whether an assessment occurs before or after alternative treatment.

Revised mNIS+7 Total Score Using a Different Algorithm to Handle Missing Components

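### The pattern-mixture algorithm in SAP 7.1 never restores observed off-treatment patisiran mNIS+7 values: it overwrites them with placebo-model draws, against its own text and SAP 3.8

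*SAP*

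**What the plan says.** SAP 7.1 first builds an intermediate dataset of all mITT patients. It carries an on-treatment flag for Month 9 and for Month 18, defined for observed as well as missing assessments; the flag is no when the assessment falls more than 60 days after the last dose.

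Step 1 then forms `DATAIN` from patients without the death flag and states: "For patisiran patients, the mNIS+7 data collected after treatment discontinuation will be excluded (set as missing"). The Month 18 rule is that, when the flag is no, "then mNIS+7 change at Month 18 will be set as missing"; Month 9 has the matching rule. The sample code reads that dataset directly ("proc mi data=DATAIN out=DATA_STEP1 seed=234 nimpute=100").

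After imputation, the text says that for the patisiran arm "the imputed scores after treatment discontinuation will be discarded and replaced by either observed non-missing values or imputed values described in the next step". The rule written to carry this out is that, for records with flag no, "then mNIS+7 change at Month 18 will be replaced by the value in DATAIN", again with a Month 9 counterpart. Step 2 imputes whatever is still missing with a model restricted to placebo observations. Step 3 draws scores for patients who died from the worst 10% of non-missing values in `DATAIN`.

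Two other places bear on this. Assumption 1c in SAP 4.3.1.3 reserves placebo-based imputation for "Patisiran patients who have missing data (either Month 9 or 18) after stopping their study treatment". SAP 3.8 says: "All efficacy data collected during study, regardless of whether before or after treatment discontinuation, will be included for analyses"; its only exception is certain endpoints after alternative FAP treatment.

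**The concern.** The restoration rule points at the dataset from which the values have just been removed. An observed off-treatment patisiran value is deleted, imputed, deleted again, and finally replaced by a placebo-model draw. An off-treatment Month 9 value goes the same way, so Month 18 is then imputed without it. The placebo arm has no such exclusion, so the same kind of observation is kept in one arm and discarded in the other.

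This analysis exists to test the primary MMRM against departures from missing at random, and it is the only one in SAP Table 1 that does so. The MMRM uses retrieved off-treatment values. If the pattern-mixture analysis discards them, a difference between the two results mixes the intended assumption about missing data with the loss of real data. Protocol 4.5.1 encourages patients who stop treatment to complete the Month 9 and Month 18 assessments so that the final analyses include them, and Protocol 6.3.2 provides the return visits.

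**Working it through.** **Trace of the algorithm.** Take a patisiran patient with an on-treatment Month 9 change of 5, an observed Month 18 change of 3 more than 60 days after the last dose, and no alternative FAP treatment.

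| Stage | Month 18, patisiran | Month 18, placebo patient in the same position |
|---|---|---|
| Intermediate dataset | 3 (observed) | observed |
| `DATAIN` | missing (flag no) | observed |
| `DATA_STEP1` | patisiran-model draw | observed |
| `DATA_STEP1_2` | value in `DATAIN`, so missing | observed |
| `DATA_STEP2` | placebo-model draw | observed |

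The observed 3 is never used. No numerical assumption enters this result. Whatever the number k of such patients, the rule as written retains 0 of k; restoring from the intermediate dataset retains k of k.

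**Design figures for scale (SAP 3.1).** Difference 8.95, SD 16, two-sided alpha 0.05, power 90%, 2:1 allocation:

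- Placebo n = 1.5 × (1.960 + 1.282)² × 16² / 8.95² = 50.4, so 51, and 153 in total. With 51 and 103 (154 in total) the t-test power is 0.901, so the plan's 154 is reproduced.
- 154 / 0.75 = 205.3, so 206, consistent with approximately 200.
- Two thirds of 200 is about 133 patisiran patients.
- Standard error of the difference at 103 and 51: 16 × √(1/103 + 1/51) = 2.74.

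**Size by simple arithmetic.** The stop rate, return rate and gap are assumptions: 15-25% stop, 30-70% of those supply a Month 18 value, and observed values differ from placebo-model draws by 4-9 points.

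- Values lost: 133 × 0.15 × 0.30 = 6.0, up to 133 × 0.25 × 0.70 = 23.3.
- Shift in the patisiran mean = stop rate × return rate × gap: 0.15 × 0.30 × 4 = 0.18, up to 0.25 × 0.70 × 9 = 1.575 points.
- In standard errors: 0.18 / 2.74 = 0.07, up to 1.575 / 2.74 = 0.57.

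**Size by simulation.** The rule as written was compared with restoration of observed values, for 133 patisiran and 67 placebo patients, 300 replicates and 10 imputations. Assumptions not in the documents: placebo Month 9 mean 12, Month 9 benefit 4.475 (half of 8.95), Month 9 SD 11, correlation 0.7, treatment stopped before or after Month 9, and returning patients keeping between -50% and 100% of the benefit.

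| Patisiran patients with an observed off-treatment Month 18 value | k | Shift in the estimated difference (design -8.95) |
|---|---|---|
| 3% | 4 | -0.29 to +0.27 |
| 5% | 7 | -0.47 to +0.51 |
| 10% | 13 | -0.89 to +0.87 |
| 20% | 27 | -1.85 to +1.82 |

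A plus sign means the apparent benefit shrinks; a minus sign means it is inflated. For patients who stop after Month 9, the placebo model carries their better Month 9 value forward with slope 0.7 × 16/11 = 1.02. The draw therefore keeps about 1.02 × 4.475 = 4.6 points, roughly half of 8.95. Patients who truly lost more than that are made to look better, and those who lost less are made to look worse.

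**The case against.** The strongest reply is that this is a dataset-label slip whose intent is plain from the neighbouring sentence: observed values were meant to be restored, and a careful programmer would restore them. `DATAIN` is introduced as a subset of the intermediate dataset before the exclusion is described, and the code is labelled as a sample. The intent is indeed clear, but reading `DATAIN` as still holding the observed values does not rescue the text. The sample code would then fit the patisiran imputation model on off-treatment data, against the stated exclusion and against assumption 1b, which bases that model on on-treatment data. The passage is inconsistent on either reading, and following the two replacement rules literally gives the wrong analysis.

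Several other points stand:

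- Fitting the patisiran model to on-treatment data only is deliberate, and control-based imputation is asymmetric by design. The fault lies only in the failed restoration.
- Off-treatment values that are truly missing are still imputed from placebo as intended, so the analysis does not lose all its purpose.
- The primary MMRM, the alpha and the testing hierarchy do not depend on this analysis.
- The upper magnitudes are generous. No return rate is given. The 25% in SAP 3.1 allows for premature discontinuation, not for patients who stop and come back. Values after alternative FAP treatment are already missing in both arms. Protocol 6.3.2 spells out the Month 18 return visit for those who stopped more than 24 weeks beforehand, and the option to stop treatment and stay on study came with protocol version 6.0. A 9-point gap is about the whole design effect. At 3-5% affected, the simulated shift is at most 0.51 points, or 0.51 / 2.74 = 0.19 standard errors.
- On Step 3, the whole-population wording in SAP 4.3.1.3 may mean only that both arms are pooled. The effect on the death draws was not quantified.

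**Conclusion.** The concern holds. As written, SAP 7.1 discards every observed off-treatment patisiran value and substitutes a placebo-model draw, contrary to its own stated intent, to assumption 1c and to SAP 3.8. That follows from the text alone. The consequence is confined to the pattern-mixture sensitivity analysis. Its size rests on assumptions about how many patients stop and return, and how they fare: a few tenths of a point if 3-5% of the patisiran arm is affected, and up to about 1.6 points (arithmetic) or 1.85 points (simulation) in the generous cases, against a design difference of 8.95. The direction is not fixed: conservative if returning patients keep more benefit than the placebo model gives them, anti-conservative if they keep less.

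**What to change.** In SAP 7.1 Step 1, keep the exclusion when fitting the patisiran model, but change both replacement rules (Month 9 and Month 18) so that off-treatment records take their value from the intermediate dataset as it stood before the exclusion, not from `DATAIN`. Step 2 then imputes only values that are truly missing. The missing-data pattern stays monotone, because the intermediate dataset already fills a missing Month 9 value when Month 18 is present. Draw the Step 3 worst-10% scores from the observed Month 18 values in that same dataset.

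The cost is a few words in the SAP and a change of dataset name in the program, with no new data. It should be settled before unblinding; afterwards, choosing between the two versions would be post hoc.
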